## 11 STATISTICAL METHODS

### 11.1 Populations

The following analysis populations are defined for the study:

**PK-evaluable Population**—all patients who received at least one dose of CO-1686 and have adequate PK assessments drawn for determination of the PK profile. Adequacy will be determined on a case-by-case basis and will be assessed prior to analysis of the blood samples.

**Food-effect PK Population**—all patients who enrolled into a food-effect PK evaluation cohort who received CO-1686 on both Day -7 and Day 1, complied with the fed and fasted requirements, and have sufficient PK data for a comparison to be made between the fasted and fed state.

**ECG/PK Comparison-Evaluable Population**—all patients in Phase 1 and Phase 2 who have received CO-1686 and have had adequate PK and ECG assessments performed for determination of the ECG effects and the relationship between PK and ECG.

**Safety Population**— all patients who have received at least one dose of CO-1686.

**DLT-evaluable Population**—all patients enrolled into Phase 1 of the study who received at least 80% of scheduled doses of CO-1686 and completed Cycle 1 of treatment, or who experienced a DLT in Cycle 1.

**Tumor-evaluable Population**—all patients who received at least one dose of CO-1686, have measurable tumor lesions at baseline, and have at least one post-baseline disease assessment.

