##### **Objective Response Rate (ORR) - Primary Endpoint**

A primary endpoint in Phase 2 of the study (objective response rate) is the best response recorded from the start of the treatment until disease progression or recurrence. The frequency and percentages of patients with a best response of CR, PR, stable disease (SD), or progressive disease (PD) will be summarized for the tumor-evaluable and safety populations enrolled in Phase 2. The response rate (CR+PR) will also be presented with frequencies and percentages.

For patients who continue treatment post-progression, the first date of progression will be used for the analysis.

The ORR will be evaluated by the investigator with the primary analysis based on investigator assessment.

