### 4 ANALYSIS POPULATIONS

**PK-Evaluable Population**—all patients who have received at least one dose of CO-1686 and have had adequate PK assessments drawn for determination of the PK profile. Adequacy will be determined on a case-by-case basis and will be assessed prior to analysis of the blood samples.

**Food-Effect PK Population**—all patients participating in the food-effect PK evaluation in Phase 1 of the study who received CO-1686 on both Day -7 and Day 1 (Cycle 1) complied with the fed and fasted requirements, and have sufficient PK data for a comparison to be made between the fasted and fed state.

**ECG/PK Comparison-Evaluable Population**—all patients in Phase 1 and Phase 2 who have received CO-1686 and have had adequate PK and ECG assessments performed for determination of the ECG effects and the relationship between PK and ECG

**Safety Population**—all patients who have received at least one dose of CO-1686.

**DLT-Evaluable Population**—all patients enrolled into Phase 1 of the study who received at least 80% of Cycle 1 scheduled doses of CO-1686 and completed Cycle 1 or who experienced a DLT in Cycle 1.

**Tumor-Evaluable Population**—all patients who received at least one dose of CO-1686, have measurable tumor lesions at baseline, and have at least one postbaseline disease assessment. Patients that died prior to receiving at least one postbaseline disease assessment will also be included.

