## 11 EFFICACY ANALYSIS

All efficacy evaluations will be conducted in patients that are centrally confirmed to be T790M positive using the efficacy-evaluable and safety populations, unless otherwise specified.

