### 15 SUMMARY OF CHANGES FROM PROTOCOL SPECIFIED ANALYSES

Due to the conditional/accelerated approval strategy, the initial MAA and NDA submission data sets will focus on the subset of patients treated at 625mg BID or 500mg BID and enrolled up to the 31st of December with data as of April 2015.

The following changes from the protocol specified analyses are contained in this SAP:

1. The patients with death before first post-baseline scan will be included in the ORR analysis with the category of 'Death before first post-baseline scan'. This means that the tumor evaluable population was changed to an efficacy analysis population including those with death before first scan
2. Clarified how ongoing patients are analyzed for ORR
3. Added the duration of treatment in patients with a CR or PR
4. PFS analyses are not included since the study is still ongoing
5. PRO analyses are not included since the study is still ongoing
6. Analyses of the time to adverse events that results in a dose reduction, interruption, or discontinuation of study drug are included.

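### The evaluable population for the primary ORR drops living patients with no post-baseline assessment, and neither planned denominator is named primary

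*SAP*

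**What the plan says.** **Who is evaluable.** Protocol 11.1 defines the tumor-evaluable population as treated patients who "have measurable tumor lesions at baseline, and have at least one post-baseline disease assessment". SAP section 4 repeats this ("have measurable tumor lesions at baseline, and have at least one postbaseline disease assessment") and adds one exception: "Patients that died prior to receiving at least one postbaseline disease assessment will also be included". SAP section 15, item 1, describes the same change by saying that "the tumor evaluable population was changed to an efficacy analysis population including those with death before first scan".

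**Which population carries the ORR.** In Protocol 11.2.4.2 the best-response categories for the primary ORR "will be summarized for the tumor-evaluable and safety populations enrolled in Phase 2". SAP section 11 restricts efficacy to centrally confirmed T790M-positive patients, analysed "using the efficacy-evaluable and safety populations, unless otherwise specified". The safety population is "all patients who have received at least one dose of CO-1686". Neither document says which of the two is primary. SAP section 4 has no entry for an efficacy-evaluable population; the reader must infer from section 15 that it is the amended tumor-evaluable population.

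**How missing responses are handled.** SAP 11.1 defines ORR as a best response of CR or PR by the investigator and gives no denominator. It adds a confirmed response rate for patients with sufficient data and classes the others as inevaluable. SAP sections 3 and 12.1 rule out imputation. No text treats an absent response as non-response.

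**The concern.** Membership of the evaluable population depends on something that happens after treatment starts. A patient who withdraws, is lost to follow-up or is too unwell to attend, and so is never re-imaged, has not responded as far as anyone can show. Removing that patient lowers the denominator and leaves the numerator unchanged. The SAP accepts this reasoning for early deaths but does not extend it to living patients.

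The study has no control arm in which the effect could cancel. The primary ORR is investigator-assessed in an open-label study, and SAP section 15 says the data sets serve a conditional or accelerated approval strategy. With two planned denominators and neither ranked, the choice of headline figure stays open until the results are known.

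**Working it through.** **1. The plan's own figure.** Protocol Table 5 reports an overall objective response of 14 (63.6%) in a column headed N = 24. A footnote bases the percentage on patients with a non-missing best response.

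- 14/22 = 63.6% (exact 95% CI 40.7 to 82.8), which reproduces the stated figure.
- 14/24 = 58.3% (36.6 to 77.9), which reproduces the PR row of the same table.

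The gap is 5.3 points. The two patients left out had not reached the end-of-Cycle-2 scan, so this shows only how sensitive the figure is to the denominator.

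**2. Who is actually excluded.** Imaging is first due at the end of Cycle 2, Days 14 to 21 of a 21-day cycle, so between study day 21 + 14 = 35 and 21 + 21 = 42. Protocol 9.6 also asks for a scan at the End of Treatment visit, 28 (±7) days after the last dose, unless there was a scan in the previous two weeks or progression on the last scan. A patient who stops on day 10 would be due that scan between day 10 + 21 = 31 and day 10 + 35 = 45. If it is done, the patient stays in the population. The excluded group is therefore living patients who have neither assessment.

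**3. Whether scans were simply not yet due.** For the 500 and 625 mg BID submission set, SAP 2.4 gives enrolment by 31 December 2014 and a data cutoff of 29 April 2015: 31 + 28 + 31 + 29 = 119 days. That is well past day 42, so a missing first scan in this set would rarely mean that it was not yet due.

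**4. Direction and size.** Let *d* be the share of treated patients who are alive with no post-baseline assessment. They contribute no responders, so

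evaluable ORR = all-treated ORR / (1 − *d*),

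which is never below the all-treated ORR.

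Inputs:
- N = 275 + 150 = 425, the planned maximum for Cohorts A and B at 500 and 625 mg BID (SAP 2.4). The number at the enrolment cut is not given.
- All-treated ORR of 60%, borrowed from the approximate rate in the Protocol synopsis, with 45% and 30% as alternatives.
- *d* = 2% and 5%. These are assumptions; the documents give no value.

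At 60%, responders = 0.60 × 425 = 255, and 255/425 = 60.0% (95% CI 55.2 to 64.7).

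| *d* | Evaluable n | Evaluable ORR (95% CI) | Gap |
|---|---|---|---|
| 2% | 416 | 255/416 = 61.3% (56.4 to 66.0) | +1.3 |
| 5% | 404 | 255/404 = 63.1% (58.2 to 67.8) | +3.1 |

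At 45% (191 responders) the gaps are +1.0 and +2.3 points. At 30% (128 responders) they are +0.7 and +1.6.

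**5. Whether the safety-population table settles it.** It has the right denominator in principle. However, Protocol 11.2.4.2 lists only CR, PR, SD and PD, and SAP section 15 adds a category only for death before the first scan. A living, unassessed patient has no category. With imputation barred, the percentage could be taken over non-missing responses, as it was in Table 5.

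**The case against.** The strongest reply has four parts.

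- **The protocol already guards against the loss.** The End of Treatment scan is asked for in all patients, and Appendix A asks for every effort to document progression after discontinuation. SAP section 4 asks for a disease assessment, which under Protocol 9.8.2.1 includes clinical examination. A reader might infer that everyone who stops for toxicity or deterioration before days 35 to 42 leaves the denominator. The documents do not support that. What stands against the reply is that Protocol 12.1 asks for End of Treatment procedures only as far as possible, so some living patients will still have no assessment. Appendix D drops the End of Treatment scan, but only under Amendment 8, which followed the June 2016 regulatory letter and so came after the April 2015 cutoff.
- **The all-treated ORR is already planned.** Measurable disease is a Phase 2 entry criterion, so for Phase 2 the centrally T790M-positive safety population is close to the denominator proposed here. SAP section 5 also tabulates population allocation, so a gap would be visible. This stands. It reduces the point to which figure leads and how missing responses are counted.
- **The SAP change reduces bias and is disclosed.** The protocol definition excluded unscanned early deaths as well. This is correct; the criticism is that the change stops short.
- **No decision threshold depends on the figure.** The documents state no null ORR, alpha or power, and ORR is descriptive. This limits the consequence, but the estimate is still the main efficacy evidence for a filing.

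**Conclusion.** The point holds in a limited form. The evaluable ORR is biased in one direction only, the plan does not say whether it or the all-treated ORR is primary, and it does not say how a missing response is counted in either. At an all-treated ORR of 60%, an assumed 2% to 5% of living, unassessed patients would add about 1 to 3 points; at lower ORRs the effect is smaller. That is within the sampling interval for 425 patients (half-width about 4.8 points), but it is systematic and does not shrink with more patients.

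Three further inferences are not supported:

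- **A shift of 7 to 10 points.** This would need *d* of 10% to 15%, for which the documents give no basis given the End of Treatment scan.
- **Table 5 hides failures.** Its two omitted patients had not reached their scan.
- **The comparison of 500 with 625 mg BID is distorted.** Protocol 5.1.3 does intend to compare ORR between dose levels, and differing early loss could matter. But nothing shows that loss differs by dose, allocation was not randomized under Amendment 7, and no test is specified. It is a possibility only.

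**What to change.** In SAP 11.1:

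- Name all treated, centrally T790M-positive patients with measurable disease at baseline as the primary ORR denominator.
- Count any such patient without a post-baseline assessment, for whatever reason, as a non-responder, and show these patients in their own row beside the existing early-death category.
- Keep the evaluable-population ORR as a sensitivity analysis.

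In SAP section 4, define *efficacy-evaluable* and use one name for it throughout. Report how many patients separate the two denominators, and why.

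The cost is wording. Both tables are already planned, and in Phase 2 the proposed denominator nearly matches the T790M-positive safety population. Where Phase 1 patients are pooled in, the measurable-disease condition needs applying, because it was not a Phase 1 entry criterion. The headline ORR may be slightly lower.

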## 5 PATIENT DISPOSITION

Patient disposition (analysis population allocation, dose group, treated, discontinued study drug, along with primary reason for discontinuation of study drug) will be summarized using frequency counts, and the corresponding percentages.

## 6 INCLUSION / EXCLUSION VIOLATIONS

The number of patients that violate each inclusion or exclusion criteria will be summarized with frequencies and percentages.

## 7 DEMOGRAPHICS AND BASELINE CHARACTERISTICS

All demographic and baseline characteristics will be summarized for the safety population.

### 7.1 Demographics

The demographic variables will be summarized with frequency tabulations that will focus on identifying the extreme values of the distributions. Descriptive statistics will also be used to summarize the quantitative variables. The demographic variables presented will include age, height, weight, gender, race, and ECOG Performance Status using the following categorizations:

- Age (years):  $\leq 50$ , 51-65, 65-80, 81-95,  $>95$ ;
- Height (cm):  $\leq 75$ ,  $>75-100$ ,  $>100-125$ ,  $>125-150$ ,  $>150-175$ ,  $>175$ ;
- Weight (kg):  $\leq 50$ ,  $>50-75$ ,  $>75-100$ ,  $>100-125$ ,  $>125-150$ ,  $>150$ ;
- Gender: Male, Female
- Ethnicity: Hispanic or Latino, Not Hispanic or Latino
- Race: American Indian or Alaska Native, Asian, Black or African American, Native Hawaiian or Other Pacific Islander, White, Other
- ECOG Performance Status: 0, 1, 2.

These categorizations may be adjusted for a variable if the majority of the data lies in only 2 or 3 of the categories.

## 7.2 Baseline Clinical Characteristics

The following variables will be summarized with descriptive statistics and may also be summarized with frequency tabulations, as indicated:

- Time since diagnosis of NSCLC (months):  $\leq 3$ , >3-6, >6-12, >12-24, >24;
- Baseline laboratory parameters: graded based on CTCAE grading
- T790M status
- Method used for detection of T790M status; local tissue test, central tissue test, or plasma test
- Molecular characterization of EGFR mutations.

## 7.3 Medical History

Medical history data will be summarized using frequency tabulations by system organ class and preferred term.

## 8 STUDY DRUG EXPOSURE AND COMPLIANCE

The following variables will be summarized:

- Number of cycles initiated (Phase 1 and 2)
- Duration of exposure (Phase 1 and 2).

The duration of exposure will be summarized with descriptive statistics and frequency counts for relevant categories. The number of cycles initiated will be investigated by summarizing the number of cycles started by each patient.

## 9 PRIOR AND CONCOMITANT MEDICATIONS

All concomitant treatments documented during the study treatment period will be summarized with frequency tabulations. Prior/concomitant medication coding will utilize World Health Organization (WHO) Drug version March 1, 2007 or later.

Separate data summaries of prior medications will be provided. Prior medications will be defined as those medications with both a start and a stop date that is before the day of the first dose of study drug administration. If either the start date and/or the stop date of the medication is missing so that it is unclear whether the medication was stopped prior to first dose of study drug administration then the medication will be included in the summary of the concomitant medications.

## 10 EFFICACY VARIABLES

### 10.1 Primary Efficacy Variables

The primary efficacy variables are the objective response rate (ORR) [CR+PR] and duration of response as determined by RECIST 1.1 criteria

## 10.2 Secondary Efficacy Variables

Secondary variables include:

- Objective response rate per independent radiology review (IRR)
- Disease control rate (DCR) per investigator and IRR
- Overall survival (OS)

## 10.3 Exploratory Efficacy Variables

Exploratory variables include:

- Time to treatment failure
- Concordance of the presence of T790M mutation in blood and tumor tissue samples

## 11 EFFICACY ANALYSIS

All efficacy evaluations will be conducted in patients that are centrally confirmed to be T790M positive using the efficacy-evaluable and safety populations, unless otherwise specified.

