	
Food-effect PK Evaluation
 
The effect of food on oral CO-1686 PK was assessed in a subset of patients.
 
PK Evaluation of Once-daily Dosing Versus Twice-daily or Three-times-daily
 
Dosing was started with once-daily (QD) dosing, and subsequently the effect of twice-daily (BID) and three-times-daily (TID) dosing on oral CO-1686 PK was assessed in a subset of patients.
 
Effect on QTc
 
In Phase 1, Serial ECG monitoring is performed: at baseline, on Cycle 1 Day 1 and Cycle 1 Day 15 (prior to dosing and at multiple time points as described in Table 13 following dosing with CO-1686) and on Day 1 of all subsequent cycles [prior to dosing and at the estimated <math>T_{max}</math> (2 hours) postdose], at the End of Treatment, and as clinically indicated in order to assess the effect of oral CO-1686 on the QTc interval. All ECGs are performed on equipment provided by the sponsor (or designee) and reviewed by site personnel and a core/central laboratory.
 
Treatment-extension Period
 
Upon completion of Cycle 1 (Safety and PK Assessment Period), Phase 1 patients could participate in an optional Treatment-extension Period, with ongoing safety and activity monitoring, which begins on Day 1 of Cycle 2. Oral CO-1686 is administered daily during this period (21-day cycles).
 
Protocol-specified treatment will continue until there is progression by RECIST Version 1.1, clinical tumor progression or unacceptable toxicity as assessed by the investigator. Patients may opt to continue to receive treatment with CO-1686 following radiographic progression as outlined in the NCCN guidelines for treatment of NSCLC with EGFR TKIs if patient provides additional consent, the investigator feels it is in the patient's best interest and with sponsor approval. In general, eligible patients may include those with asymptomatic systemic progression or locally symptomatic progression, such as brain metastases amenable to local treatment, with concomitant asymptomatic systemic progression or continued systemic disease control. Patients will undergo serial assessments for anti-tumor efficacy, drug safety, and patient reported outcomes. Serial blood sampling for longitudinal quantitative assessment of ctDNA will be conducted. Following disease progression on CO-1686, patients can consent to participate in an optional additional biopsy before subsequent-line therapy is initiated.
 
As of 6 March 2014, 49 patients are continuing to receive treatment in Phase 1 of this study.
 
Part 2 - Phase 2
 
The additional dose levels added to cohorts A and B and increased patient numbers introduced in Amendment 6 allows a comprehensive assessment of dose and response across doses that have exhibited clinical activity to date. The addition of Cohort C will provide an estimate of activity in patients with a positive T790M local test, but discordant central test results or missing central test results due to inadequacy of the tissue specimen by central test, and will allow CO-1686 treatment based on a local T790M positive result only.

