Amendment 6 allowed for the addition of 2 doses levels of CO-1686 (500 mg BID and 625 mg BID) in patients who have progressed on initial EGFR inhibitor therapy (Cohort B), and in patients with later line disease (Cohort A). Patients will no longer enroll in the 750 mg BID dose level for Cohorts A and B, but will be assigned to receive either 625 mg BID or 500 mg BID by the sponsor. Patients who are already receiving 750 mg BID will continue at this dose. Patients will be allocated to Cohorts A and B based on the results of central EGFR testing for T790M status (Therascreen, Qiagen). As it is expected that some patients who test negative for T790M with the central test will have tested positive using local tests, a new cohort (Cohort C, 625 mg BID) has been added to assess activity of CO-1686 in such cases. This last cohort will also be open to patients in whom the central test did not provide an EGFR result because the biopsy specimen was not suitable for analysis by the central lab. Building on the observed efficacy of CO-1686, a more precise estimate of optimum dose will be derived from the augmented cohorts.

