#### **5.1.3 Phase 2**

This phase of the study will consist of a screening phase to establish study eligibility and document baseline measurements, an open-label treatment phase, in which patients will receive CO-1686 to ascertain safety and efficacy until protocol-defined disease progression. Each 21-day period of treatment will represent one cycle, with dosing initiated on Cycle 1 Day 1. Eligible patients are those who are confirmed by the sponsor's central laboratory (Cohorts A and B) or by local assessment (Cohort C) to have the T790M mutation in FFPE tumor tissue.

The assessments for patients in each Phase 2 cohort will be identical.

Enrollment into Part 2 was initiated in February 2014 under Amendment 4 when a RP2D of 750 mg BID was selected. This initial RP2D of 750 mg BID was selected based on early Phase 1 efficacy data and two expansion cohorts (Cohorts A and B) are currently enrolling at this dose. As the Phase 1 efficacy data matured, the recommended dose was adjusted to 625 mg BID, and under this amendment patients will no longer enroll in the 750 mg BID dose level for Cohorts A and B, but will be assigned by the sponsor to receive either 625 mg BID or 500 mg BID in these cohorts. Patients who are already receiving 750 mg BID will continue at this dose. Cohort A comprises later-line patients who have previously received one or more prior EGFR TKI, and irrespective of the number and order of previous lines of NSCLC therapy, and who are not eligible for Cohort B. Cohort B comprises earlier-line patients who have had radiologic progression on one prior single agent EGFR TKI for advanced/metastatic NSCLC, and have had

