- Only patients with evidence of a positive T790M mutation result from a local lab but with an insufficient specimen for central lab analysis (judged by the central lab analysis) or a negative central T790M mutation result from the same biopsy specimen collected within 60 days of treatment with CO-1686.

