## 2.3 Trial Design and Study Procedures

This study will include 2 parts:

- Phase 1: Dose-escalation Period with 21-day cycles; optional Treatment Extension Period starting on Day 22
- Phase 2: Evaluation of activity and safety in patients with the T790M EGFR mutation who have:
  - Cohort A
    - Progressed on EGFR directed therapy (irrespective of the number and order of previous lines of NSCLC therapy) (Dose levels of 750 mg BID, 625 mg BID and 500 mg BID)
    - or
    - Cohort B
      - Progression on the first single agent EGFR directed therapy received and also had no more than one previous line of chemotherapy (Dose levels of 750 mg BID, 625 mg BID and 500 mg BID)
      - or
      - Cohort C

- Signed consent for the study, and fulfils eligibility, but with discordance between local (T790M positive) and central (T790M negative) T790M results, or had no central test result due to inadequacy of the tissue specimen and known to be T790M positive by local test (Dose level of 625 mg BID).

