### 11.1 Primary Efficacy Analysis

The primary efficacy endpoint of ORR is defined as a best response of CR or PR as determined by the investigator. Response and/or progression are evaluated using the RECIST 1.1 criteria. The ORR will be summarized with frequencies and percentages.

The confirmed response rate will be calculated for patients with sufficient data to determine if the patient has a confirmed response or has progressive disease, otherwise patients will be classified as inevaluable for confirmed response at the time of analysis.

As a secondary endpoint, ORR will be evaluated per the IRR.

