### 11.2 Secondary Efficacy Analyses

#### 11.2.1 Duration of overall response

The duration of overall response is measured from the time measurement criteria are met for CR or PR (whichever is first recorded) until the first date that recurrent disease or PD is objectively documented (taking as reference for PD the smallest measurements recorded since the treatment started).

The duration of overall CR is measured from the time measurement criteria are first met for CR until the first date that recurrent disease is objectively documented.

The duration of overall response and the duration of overall CR will be summarized with Kaplan-meier methodology. Only patients with a PR and/or CR will be included in the summary.

The duration of response will be summarized for the both the investigator assessment and the independent radiology review.

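### SAP 11 removes all Cohort C patients from the ORR and duration-of-response summaries that the protocol plans for Phase 2 Cohorts A to C, and SAP 15 does not list the change

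*SAP*

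**What the plan says.** **Analysis set.** SAP 11 states that "efficacy evaluations will be conducted in patients that are centrally confirmed to be T790M positive using the efficacy-evaluable and safety populations, unless otherwise specified". SAP 11.1 defines the primary ORR as an investigator-assessed best response of CR or PR and adds: "The ORR will be summarized with frequencies and percentages". SAP 11.2.1 summarizes duration of response by Kaplan-Meier and adds: "Only patients with a PR and/or CR will be included in the summary". Neither subsection names a different patient set.

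**Cohort C.** Protocol 6.2 admits to Cohort C only patients with a positive local result but "with an insufficient specimen for central lab analysis (judged by the central lab analysis) or a negative central T790M mutation result". SAP 2.3 describes the same group as having "discordance between local (T790M positive) and central (T790M negative) T790M results", or no central result because the tissue was inadequate.

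**Purpose of Cohort C.** The protocol synopsis says: "The addition of Cohort C will provide an estimate of activity in patients with a positive T790M local test, but discordant central test results". Protocol 3.5.3 says "a new cohort (Cohort C, 625 mg BID) has been added to assess activity of CO-1686 in such cases". Protocol 5.1.3 counts as eligible those confirmed centrally (Cohorts A and B) "or by local assessment (Cohort C) to have the T790M mutation in FFPE tumor tissue".

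**Protocol analysis.** Protocol 11.2.4.2 is headed as covering Phase 2 Cohorts A to C. It makes ORR and duration of response primary endpoints and summarizes ORR in the tumor-evaluable and safety populations enrolled in Phase 2. Neither endpoint has a central-test condition.

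**Declared changes.** SAP 15 lists six numbered changes from the protocol analyses and notes the focus on the 500 and 625 mg BID patients. The central-positive restriction is not among them.

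**The concern.** The protocol opened Cohort C to learn whether the drug is active when the local test is positive and the central test is negative or gives no result. Under the SAP default these patients drop out of both primary-endpoint summaries. What is left is a permission to run subgroups. Whether a Cohort C response rate is reported can therefore be decided after the responses are known, in an open-label study where the investigators' assessments are visible as they accrue.

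The second problem is disclosure. A reader who relies on SAP 15 to learn how the SAP departs from the protocol would not learn that one of the three Phase 2 cohorts has left the main efficacy summaries.

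**Working it through.** 1. **Reproduce the planned total (SAP 2.4).** Cohort A: 40 + 275 = 315. Cohort B: 40 + 150 = 190. Cohort C: 100. Sum: 315 + 190 + 100 = 605, the stated Phase 2 figure. Adding 110 for Phase 1 gives 715, as stated.

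2. **Apply the SAP 11 condition.** Membership requires a positive central result. Cohort C requires a negative or absent central result (Protocol 6.2, SAP 2.3). No patient can satisfy both, so all of Cohort C is excluded. At most 605 − 100 = 505 Phase 2 patients remain.

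3. **Size.** Share of Phase 2: 100/605 = 16.5%. Phase 2 patients planned at 500 or 625 mg BID: 275 + 150 + 100 = 525, and 100/525 = 19.0%. These are enrolment caps. The documents do not give the number of Cohort C patients in the submission data set.

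4. **Look for an exception in the SAP.**
   - SAP 11.1 and 11.2.1: none.
   - SAP 12.4: subgroups by T790M status and by detection method are allowed but not required. Cohort is not one of the nine listed variables.
   - SAP 3: summary tables are to cover all treated patients. This is a general convention; SAP 11 is the specific rule for efficacy, and SAP 3 names no Cohort C response analysis.
   - SAP 11.3.1: a waterfall plot for all patients and relevant subgroups. It shows change in tumor size and gives neither ORR nor duration of response.
   - SAP 2.4: all patients at 500 or 625 mg BID enrolled by 31 December 2014 are used for efficacy and safety conclusions. This names no Cohort C analysis, and its relation to the SAP 11 filter is not stated.

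5. **Compare with SAP 15.** Item 1 changes the ORR population, but only to add patients who died before the first post-baseline scan. Items 4 and 5 declare that PFS and patient-reported outcomes are left out because the study is ongoing. No item mentions central confirmation or Cohort C.

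6. **What a Cohort C summary could show.** The exact (Clopper-Pearson) 95% limits for x responders among n are the 0.025 quantile of Beta(x, n − x + 1) and the 0.975 quantile of Beta(x + 1, n − x). The response rates and the smaller n values are assumptions that show the range.

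| n | Assumed ORR | Exact 95% CI |
|---|---|---|
| 25 | 40% (10/25) | 21.1% to 61.3% |
| 50 | 40% (20/50) | 26.4% to 54.8% |
| 100 | 20% (20/100) | 12.7% to 29.2% |
| 100 | 40% (40/100) | 30.3% to 50.3% |
| 100 | 60% (60/100) | 49.7% to 69.7% |

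Near the cap the estimate would be informative. At 25 patients it would be wide but still worth reporting.

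**The case against.** The best case for the SAP has four parts.

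- **Scope.** SAP 1 limits this version to what goes into the NDA and MAA, and no text requires Cohort C results there. That may explain the restriction. It does not disclose it, and SAP 15 does declare other omissions tied to the timing of the submission.
- **A T790M filter is needed.** SAP 3 allows Phase 1 and Phase 2 dose groups to be shown together, and Phase 1 enrolled regardless of T790M status. Some filter is therefore needed to match the Phase 2 primary objective in SAP 2.2.1. This stands, but that objective refers to patients with a T790M mutation and does not require central confirmation.
- **All-patient displays exist.** SAP 3 and the waterfall plot do commit to displays that could include Cohort C. It would be wrong to say that the SAP shows nothing on these patients. Neither, however, specifies a Cohort C ORR or duration of response.
- **Limited consequence.** The Phase 2 response summaries are descriptive, with no stated hypothesis or alpha. That stands, and it is why the remedy is small.

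A reader might also infer that the protocol promises a separate Cohort C duration-of-response table. It does not: it plans that endpoint across Cohorts A to C. Its only response analysis specific to Cohort C is the futility look at the first 12 patients (Protocol 11.3).

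**Conclusion.** The point holds. SAP 11 takes every Cohort C patient, up to about 100 of 605 planned in Phase 2 (16.5%), out of the ORR and duration-of-response summaries that the protocol plans for Cohorts A to C. What remains is optional, and SAP 15 is silent. This rests on the wording alone; the percentages assume that Cohort C fills to its cap.

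Two stronger readings are not supported. One is that the sponsor abandoned the Cohort C analysis: the SAP covers the submissions only and leaves subgroups open. The other is that the headline ORR is distorted by some number of points. That would need the actual Cohort C enrolment, its response rate, and a reading of SAP 2.4 as an efficacy population; that paragraph can equally be read as setting only enrolment and data cutoff dates. The documents supply none of these.

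**What to change.** - **SAP 11:** keep the centrally confirmed positive set as primary. Commit to a separate descriptive summary for Cohort C of ORR, with an exact 95% CI, and of duration of response.
- **SAP 2.4, 3 and 11:** state in consistent terms which patients count for efficacy conclusions, and whether SAP 2.4 sets only the enrolment and data cutoff.
- **SAP 15:** list the central-positive restriction as a change from the protocol and give the reason.

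The separate Cohort C table with an interval goes a little beyond the protocol, which asks for frequencies and percentages across Phase 2, but it delivers the activity estimate for which the cohort was opened. The cost is a few sentences and one or two tables from data already collected, with no new patients or procedures.
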